1. INTRODUCTION AND RATIONALE

Cellulitis

Cellulitis is a common acute, spreading pyogenic inflammation of the skin (dermis) and subcutaneous tissue, usually complicating a wound, ulcer or dermatosis.¹ Erysipelas, while originally a separate disease entity with a well-defined raised edge and more prominent systemic symptoms, is now considered a manifestation of cellulitis, due to the ability of cellulitis to extend to the dermal layers, making it practically impossible to make a meaningful distinction². Cellulitis is considered to be severe if the patient is admitted to the hospital to receive intravenous antibiotics (please refer to Appendix I for the background of the definition of cellulitis used). Cellulitis is among the most frequent infections leading to hospitalization.^{3,4} The incidence of bacterial skin infection in the Netherlands has increased considerably in recent years, up to 32 per 1000 patients per year (Landelijk Medische Registratie, 2012). This is probably due to an increase in both the elderly population and the number of patients with immunosuppressive conditions such as diabetes.⁵ In addition, clinical relapse occurs in 12 to 20% of patients.^{6,7} 6% of all patients with a bacterial skin infection who consult the general practitioner will be hospitalized. In the USA alone it is estimated that cellulitis results in more than 600,000 hospitalizations per year, which represents more than a 50% relative increase in the past decade.³ In the Netherlands the diagnosis bacterial cellulitis and erysipelas are made approximately 28.000 times each year, resulting in over 2500 hospitalizations. Total health-care associated costs, mostly due to costs of hospitalisation, were estimated to be over 17 million euro each year during 1998-2000⁸.

Antibiotic treatment

For cellulitis initial antibiotic treatment is given intravenously (i.e., the patient is hospitalized) if the lesion is spreading rapidly, if the systemic response is prominent with fever and general malaise, when oral antibiotic therapy has failed, or if there are coexisting conditions such as immunodeficiency, neutropenia, asplenia or pre-existing edema.^{1,3} As most cases of cellulitis are caused by Gram-positive bacteria (*Streptococci* and *Staphylococcus aureus*), beta-lactam antibiotics with activity against penicillinase-producing *S. aureus* are the drugs of choice. In the Netherlands, flucloxacillin is the recommended treatment regimen for hospitalized patients with cellulitis (dose: po 500 mg 4dd1 or iv 1000 mg 4dd1; www.swab.nl). Clindamycin is given in case of an allergy to beta-lactam antibiotics.⁹ Recommended treatment duration for all antibiotics is 10 to 14 days.⁹ However, the duration of therapy required remains ill defined: the need for 10-14 days of treatment is not evidence based. A recent systematic review concluded that there is little evidence for duration of antibiotic therapy¹⁰. Of note, antibiotic resistance of *S. aureus* (MRSA, Methicillin Resistant *S. aureus*,) is an increasing problem in many parts of the world. In the Netherlands, MRSA prevalence is still well below 5%.^{9,11}

Justification of therapeutic intervention

It has previously been postulated that after several days of therapy residual symptoms persist due to inflammation rather than active infection, which means that prolonged antibiotic therapy is not indicated. This notion is underscored by a clinical study in which 5 days of antibiotic therapy proved to be equally effective for uncomplicated cellulitis in an outpatient setting compared to 10 days of therapy.¹² In addition, more recent studies have shown that antibiotic treatment for pneumonia^{13,14}, urinary tract infections^{15,16} and acute

pyelonephritis¹⁷ can safely and significantly be shortened. Still, optimal treatment strategies in terms of duration of antibiotic therapy for cellulitis warranting hospitalization are still ill defined. In light of the aforementioned studies, it is likely that the currently advised 10-14 days of antibiotic therapy can be safely and significantly reduced as well. It is important that evidence-based strategies are developed to optimize outcome, antibiotic use, and use of health care resources.

Hypothesis

We hypothesize that there is no difference in outcomes when patients hospitalized with cellulitis are treated with either a short-course (6 days) or standard-course (12 days) of antibiotics.

2. OBJECTIVES

2.1 Primary objective

- To determine whether 6 days of flucloxacillin has equal efficacy compared to 12 days in patients hospitalized with cellulitis who after 5 days of initial therapy have substantially improved, defined as absence of fever (temp $> 38.0^{\circ}\text{C}$) and improvement in cellulitis severity score.

2.2 Secondary objectives

- To assess differences in the frequency of relapse by day 90
- To assess differences in (A) speed of improvement of symptoms and (B) quality of life
- To assess the effects of 6 days of antibiotics compared to 12 days on total antibiotic use and health care costs

2.3 Tertiary objectives

- To analyse inflammatory and microbiological parameters in the (epi)dermis and blood during cellulitis, to explore markers of disease severity, determinants of therapeutic failure, and tools for pathogen detection

3. STUDY DESIGN

3.1 Design

The DANCE study is a prospective, randomized, observer, physician and patient blinded, placebo-controlled, multicentre non-inferiority trial with two parallel groups. Patients hospitalized with cellulitis and responding to initial therapy, defined as absence of fever (temp > 38.0°C) and improvement in cellulitis severity score (self-reported or investigator-assessed) by day 5, will be randomized with a 1:1 allocation into one of two groups, who will receive different treatments after the 6th day:

- Regular treatment group: after the initial 6 days of flucloxacillin, another 6 days of oral flucloxacillin.
- Intervention group: after the initial 6 days of flucloxacillin, 6 days of oral placebo.

Study protocol is based on the SPIRIT 2013 guidance for clinical trial protocol development¹⁸.

3.2 Duration and setting

The estimated duration of the study is three and a half years (see also 3.4 and 4.1); for individual patients the study duration will be 90 days. The trial will be performed in the Internal Medicine and Dermatology departments of the hospitals mentioned above, and their respective outpatient clinics after discharge. Depending on patient preference and availability of clinical examination rooms at the outpatient clinics, the dedicated research nurse/investigators can also visit participants at their home address. Informed consent will be obtained by the dedicated research nurse/ investigators, after the attending physician inquires about willingness to participate in a clinical trial.

3.3 Time schedule of study procedures for participants

	Day 0	Day 2-3	Day 5-6	Day 14-15	Day 28-29	Day 90
Informed consent	X					
In- and exclusion criteria	X					
Physical examination	X		X	X	X	
Laboratory measurements (usual care)	X					
Venous puncture	X	X	X	X	X	
Skin biopsy (see chapter 7)	X					
Clinical cellulitis score	X	X	X	X	X	
Self assessment score (0-10 scale)	X	X	X	X	X	X
SF-36 questionnaire & EQ-5D	X				X	X
Health care utilization questionnaire			X		X	X
Skin swabs (see chapter 7)	X			X		

Table 1. Time table of study procedures for participants

Up to day 28-29, patients will be evaluated face to face either in the clinic or at home. Self assessment scores and questionnaires to be performed on day 90 will be mailed to patients beforehand. On day 90, the investigators will review the answers and scores by telephone. Laboratory measurements collected through usual care will be collected when available. In exceptional cases, where inclusion would be hampered by people's willingness or ability to have so many follow-up visits, the decision can be made by the investigators to perform the day 28-29 visit solely by telephone. In this case the primary endpoint, questionnaires and medication information would be assessable. Physical examination, cellulitis severity score measurement and blood collection will not be possible.

The above table displays the ideal time schedule for participants. However, patients can be included until 72 hours after admission. When patients are included during 24-72 hours, the day 2-3 visit is skipped. The check for improvement on day 5-6 then also allows for self-reported improvement as marker for clinical improvement, due to the investigator not being present at the time when the disease was likely at its most severe. Self-reported improvement is also rated using the seven aspects of the cellulitis severity score; patients will be asked if they think that they have improved, taking all those aspects into account.

[figure not shown]

Figure 1. Flow diagram for study participants**3.4 Time schedule of the study**

Months 1-4:	Preparation of study and obtaining ethical approval
Months 5-44:	Enrolment of patients
Month 44:	Last patient enrolled
Month 47:	Last follow-up visit of last enrolled patient
Months 47-48:	Analysis of results

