7. METHODS

7.1 Study endpoints

7.1.1 Main study endpoint

The primary endpoint is resolution of cellulitis at 14-15 days, defined as disappearance of warmth and tenderness at the site of infection, with substantial improvement in erythema and edema, and without recurrence by day 28-29, defined as the need of additional antibiotic therapy for cellulitis.

This endpoint is in accordance with the study by Hepburn et al¹², and assumes that erythema and edema take longer to resolve than warmth and tenderness as seen in clinical practice.

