7.1.2 Secondary study endpoints

- Resolution of cellulitis at 14-15 days, defined as the absence of fever and an improvement of the combined symptom score of warmth, tenderness, erythema and edema by 2 or more points since patient inclusion (or it has reached 0), and without recurrence by day 28-29, defined as a stable or further improved combined symptom score, absence of fever and no need of additional antibiotic therapy for cellulitis.
 - A per protocol analysis of this endpoint (see paragraph 9.1).
 - Sensitivity analyses with two modifications to the day 28 criteria:
 - Resolution of cellulitis at 14 days, defined as the absence of fever and an improvement of the combined symptom score of warmth, tenderness, erythema and edema by 2 or more points since patient inclusion (or it has reached 0), and with further improvement of the combined symptom score of 1 or more point(s) (or it has reached 0), absence of fever, and no need of additional antibiotic therapy for cellulitis by day 28
 - Resolution of cellulitis at 14 days, defined as the absence of fever and an improvement of the combined symptom score of warmth, tenderness, erythema and edema by 2 or more points since patient inclusion (or it has reached 0), and with further improvement of the combined symptom score of 2 or more point(s) (or it has reached 0), absence of fever, and no need of additional antibiotic therapy for cellulitis by day 28
- Recurrence of cellulitis by day 90 after inclusion, defined as the need of additional antibiotic therapy for cellulitis
- Speed of recovery, as determined by improvement in cellulitis severity score, and self assessment of subjective pain and swelling on Visual Analog Scales scales (0-10), assessed at baseline (day 0), days 2-3, 5-6, 14-15, 28-29 and 90 (day 90 self-assessment only)¹²
- Mean health-related Quality of Life (using the Dutch SF-36 questionnaire and the EQ-5D) at day 0, 28-29 and 90.

- Health care resource utilisation, as determined by total antibiotic use and effect on direct and indirect health-care associated costs

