7.3.2 Cellulitis severity score

The severity of cellulitis will be graded at day 0, 2-3, 5-6, 14-15 and 28-29 using a clinical scoring sheet, in which the investigators assign an assessment (none, mild, moderate, or severe) to each of the following parameters: erythema, warmth, tenderness, edema,

ulceration, drainage, and fluctuance. Grading of each will be standardized among investigators at the beginning of the study by simultaneous readings. The grading designations none through severe are converted into a numerical value of 0 to 3 and these numbers were added to create a physician composite score for purposes of analysis (maximum score 21). This scoring system is the same as used in the most recent therapy duration study.¹² This will allow for measuring of objective (investigator-evaluated) improvement.

Two investigators (the PhD student and the trial nurse) will be responsible for data collection throughout the study. To minimize inter-observer variation and to promote data quality, initial patient assessment will be performed simultaneously by both investigators, and later independently and scores compared/evaluated. When five patients have been assessed independently, resulting in identical scores from both investigators, the investigators will start assessing patients on their own. After 100 patients have been assessed by a single investigator, the investigators will again assess five patients together, to compare scoring and thus improve data quality. During the course of the trial it will be evaluated if additional investigators need to be recruited, due to possible heavy workload and time spent on traveling between sites. Additional investigators will be trained by the PhD student in similar fashion as the trial nurse, with simultaneous and subsequent independent scoring as described above.

Patient self assessment scores will be performed at day 0, 2-3, 5-6, 14-15, 28-29 and 90 by visual Analog Scales (VAS) scores (rated 0-10) in order to determine the amount of pain and swelling patients experience accounting for subjective (patient-evaluated) improvement.

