9. STATISTICAL ANALYSIS

9.1 General considerations

For the modified intention to treat analysis, all randomized patients who received at least one dose of study medication will be included. Missing data will be handled with multiple imputation, due to its nature of giving standard errors and P values that incorporate missing-data uncertainty²².

For the per protocol analyses, only randomized patients whose compliance was clear, and who received at least four days of trial medication (in clinical successes), or one day of trial medication (in clinical failures) will be included.

For the per protocol analysis of our primary outcome, patients are considered clinically cured if there is resolution of cellulitis at 14 days defined as disappearance of warmth and tenderness at the site of infection, with substantial improvement in erythema and edema, and without recurrence by day 28, defined as the need of additional antibiotic therapy for cellulitis. Clinical failure is defined as the persistence or progression of signs and symptoms of the acute process after randomization, or the inability to complete the study owing to adverse events. The response is deemed indeterminate when the patient (i) received less than 80% of the study drug for reasons other than clinical failure, (ii) acquired a concomitant infection outside of the skin requiring antibiotic treatment, (iii) was lost to follow-up, or (iv) died unrelated to the primary diagnosis.

For the per protocol analysis of our first secondary outcome (paragraph 7.1.2), patients are considered clinically cured if there is resolution of cellulitis at 14 days, defined as the absence of fever and an improvement of the combined symptom score of warmth, tenderness, erythema and edema by 2 or more points since patient inclusion (or it has reached 0), and without recurrence by day 28, defined as a stable or further improved combined symptom score, absence of fever and no need of additional antibiotic therapy for cellulitis. The response is deemed indeterminate when the patient (i) received less than 80% of the study drug for reasons other than unblinding / requiring new antibiotics for cellulitis / being unable to continue due to adverse effects, (ii) acquired a concomitant infection outside of the skin requiring antibiotic treatment, (iii) was lost to follow-up, or (iv) died unrelated to the primary diagnosis. Those whose outcomes are not cured or indeterminate are considered clinical failures.

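### A telephone-only day 28-29 visit leaves the first secondary endpoint unmeasured in patients who are apparently well, and read literally the per-protocol rule in 9.1 scores them as clinical failures

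*Combined protocol and SAP*

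**What the plan says.** Section 3.3 makes face-to-face assessment the rule up to day 28-29, with an exception where the burden of visits would hamper inclusion: "the decision can be made by the investigators to perform the day 28-29 visit solely by telephone". It then states what survives, "In this case the primary endpoint, questionnaires and medication information would be assessable", and what does not, "Physical examination, cellulitis severity score measurement and blood collection will not be possible". The first secondary endpoint appears in neither list.

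The primary endpoint (7.1.1) has a day-28 part that rests on antibiotic need alone: "without recurrence by day 28-29, defined as the need of additional antibiotic therapy for cellulitis".

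The first secondary endpoint (7.1.2) asks for more. Its day-28 part, absence of recurrence, is "defined as a stable or further improved combined symptom score, absence of fever and no need of additional antibiotic therapy for cellulitis". The two sensitivity versions are stricter on the same score; the milder one reads "with further improvement of the combined symptom score of 1 or more point(s) (or it has reached 0), absence of fever", and the other asks for 2 points. Section 7.3.2 describes a scoring sheet "in which the investigators assign an assessment (none, mild, moderate, or severe) to each of the following parameters", so the score comes from an examiner.

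Section 9.1 gives multiple imputation as the missing-data method, in the paragraph that defines the modified intention-to-treat set. For the per-protocol analysis of the first secondary outcome it lists four routes to an indeterminate response: too little study drug, a concomitant infection outside the skin, loss to follow-up, and unrelated death. It closes with "Those whose outcomes are not cured or indeterminate are considered clinical failures".

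**The concern.** A patient can meet the day-14 criteria, take no further antibiotics, be reached by telephone at day 28 and report being well, and still lack the score and temperature that the endpoint needs. That patient cannot be shown to be cured. The patient was followed up, so loss to follow-up does not apply, and the other three indeterminate reasons do not apply either. The closing rule then leaves one category, failure.

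The failure would come from the way the visit was held. It would lower cure in both arms, dilute any real difference in failure rates, and bias the comparison if telephone visits were unevenly spread. Table 3 in 9.4 gives this endpoint, including its per-protocol analysis, a non-inferiority hypothesis, and in a non-inferiority setting dilution is not a conservative error.

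**Working it through.** **1. Which telephone patients are affected**

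| Telephone patient at day 28 | First secondary endpoint | Per-protocol class under 9.1, read literally |
|---|---|---|
| Did not meet the day-14 criteria | Known failure | Failure, correctly |
| Met day 14, needed antibiotics by day 28 | Known failure | Failure, correctly |
| Met day 14, no further antibiotics | Not determined: score and temperature unmeasured | Failure, by the closing rule |

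(The table assumes that no indeterminate reason applies.) Only the third row is affected. For the primary endpoint the same patient is fully classifiable, because antibiotic status can be obtained by telephone. The per-protocol text for the primary endpoint defines failure by persisting or progressing signs, or by inability to complete the study because of adverse events. It has no equivalent catch-all.

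**2. The plan's own figure**

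Inputs from 4.4: success 85% in both arms, limit 10 points, one-sided 0.05, power 80%.
n per arm = (1.645 + 0.842)² × 2 × 0.85 × 0.15 / 0.10² = 157.7, rounded up to 158; total 316. This reproduces. It rests on the primary endpoint, so the present point does not touch it.

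**3. Effect on the observed cure rate**

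Assumptions: true cure 85%, borrowed from 4.4; all 316 patients in the per-protocol set; a telephone share f, equal in both arms and unrelated to outcome. The documents give no f, so a range is shown.
Observed cure = 0.85 × (1 − f). Well patients scored as failures = 316 × f × 0.85.

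| f | Well patients scored as failures | Observed cure |
|---|---|---|
| 2% | 5.4 | 83.3% |
| 5% | 13.4 | 80.8% |
| 10% | 26.9 | 76.5% |

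The true per-protocol set will be smaller than 316, which lowers the counts but not the percentages.

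**4. Effect on the contrast when shares are equal**

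Table 3 specifies a chi-squared test and a relative risk here, without saying whether the risk is of cure or of failure. Take true cure of 85% and 75% as an illustration.
- Relative risk of cure: the factor (1 − f) cancels, so the ratio is unchanged.
- Relative risk of failure: 25/15 = 1.67 with no telephone visits. At f = 5% it is (1 − 0.7125)/(1 − 0.8075) = 28.75/19.25 = 1.49. At f = 10% it is (1 − 0.675)/(1 − 0.765) = 32.5/23.5 = 1.38.
- Risk difference: 10 points becomes 10 × (1 − f), that is 9.5 and 9.0 points.

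**5. Effect when shares differ**

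Shift in the cure difference = 0.85 × (difference in telephone share). A 5-point difference in share gives 4.25 points. In counts, 5% of 316 is about 16 patients:
- split 8/8: no shift
- split 10/6: 0.85 × 4/158 = 2.2 points
- split 12/4: 0.85 × 8/158 = 4.3 points. By chance alone, a split at least this uneven in either direction has probability about 0.077.

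**The case against.** Four points on the other side carry weight.

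- **Imputation may already cover this.** An unmeasured score is missing data rather than an observed non-cure. The imputation sentence stands in a section of general considerations, and nothing in it expressly limits it to one analysis set. That reading is available. But the per-protocol paragraphs set out their own classification without mentioning imputation, and the closing rule would classify the patient before anything was imputed. What stands is an ambiguity whose literal reading gives the wrong answer. A reader might infer that the two analyses are certain to treat the same patient in opposite ways; the text does not settle that.

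- **The endpoint is not lost for every telephone patient.** A reader might infer from 3.3 that it is. Those who missed the day-14 criteria or needed antibiotics are known failures, and the modified intention-to-treat analysis has a stated remedy for the rest.

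- **No margin is stated for the affected analysis.** A reader might set the shifts above against the 10-point limit. That limit belongs to the sample-size calculation, and Table 3 gives this per-protocol analysis a relative risk with no margin. The documents therefore do not support a claim about its type I error or power.

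- **Telephone visits should be rare and balanced.** Section 3.3 calls them exceptional, 5.5 favours home visits, and patients, physicians and observers are blinded (3.1). The stated trigger is visit burden, not response. Nothing in the documents points to differential use, so imbalance beyond chance is not to be presumed. However, no cap or expected frequency is given, and blinding does not prevent the dilution in step 4.

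**Conclusion.** The point holds for a defined group: telephone patients who met the day-14 criteria and reported no further antibiotics. For them 7.1.2 cannot establish cure on the first secondary endpoint or either sensitivity version. In the per-protocol analysis of that endpoint, 9.1 read literally counts them as failures. This is a flaw in a stated rule rather than only missing detail.

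The reach is limited to a secondary endpoint; the primary endpoint and the total of 316 stand. The size depends wholly on an unstated telephone share. If visits are as exceptional as 3.3 intends, the effect is small: under the assumptions above, a 2% share lowers observed cure by 1.7 points (85.0% to 83.3%). At 5% the loss is 4.25 points and at 10% it is 8.5. The correction is worth making because it is cheap and can be fixed before anyone knows the allocation.

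**What to change.** Before unblinding, amend 9.1 for the first secondary endpoint and both sensitivity versions, with the same rule in the modified intention-to-treat and per-protocol analyses:

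1. State that an unmeasured day-28 symptom score or temperature is missing data, not failure.
2. Multiply impute only those components. Use the day-14 status and the day-28 antibiotic status as observed, so that known failures remain failures.
3. Limit the closing failure rule to patients whose day-28 components were measured or who are already known failures.
4. Report the number of telephone day 28-29 visits by arm.

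A simpler-looking alternative is to call telephone patients without further antibiotics indeterminate. It should be avoided. It would remove patients already known to have failed at day 14, and it makes exclusion depend on outcome. If every failure were an antibiotic failure, a 5% telephone share would give observed cure of 0.8075/0.9575 = 84.3% instead of 85%.

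The cost is a short addition to 9.1, some extra analysis work, and reliance on the imputation model for what should be a few patients. Because 9.1 sets a different minimum of trial medication for successes and for failures, the amendment should also say how per-protocol membership is decided when a patient's status is imputed.
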